Skin and soft tissue infection	L00-L06	
Mycoses	B35-B45	
Pneumonia	J10.0, J11.0, J12-J18	
Age (in 5 year categories)		
Hospital admission in past 6 months		
Gout or other crystal-induced arthropathy	M10, M11	1
Falls	N/A	1
Muscoskeletal problems	G45, M12-M14, M24, M25, M36, M43, M46, M47.1, M47.8, M50-M54, M67.8, M80, M81. M84.3, M84.4, M96.1, R26.2, R29.8, Z87.3	
Urinary tract infection	N10, N30, N34, N39.0	1

• Alcohol abuse:

ICD-GM: F10

BAYER E R

- Anemia: ICD-GM: D50 – D53, D63, D64.9
- Aortic plaque: ICD-GM: I70.0
- Coronary heart disease
 - Angina pectoris:
 - ICD-GM: I20
 - o Myocardial infarction:
 - ICD-GM: I21 I23, I25.2
 - Acute ischemic heart diseases:
 - ICD-GM: I24
 - Chronic ischemic heart disease:
 - ICD-GM: I25 (excl. I25.2)
 - Coronary artery bypass graft(s) :
 - ICD-GM: Z95.1
 - OPS: 5361, 5362
 - o Percutaneous coronary intervention:
 - OPS: 8837
- Dementia: ICD-GM: F01 – F03, G30, G31.0
- Depression:
 - ICD-GM: F31, F32 F34, F39, F43,1, F43.2
- Diabetes mellitus: ICD-GM: E10 - E14
- Drug abuse: ICD-GM: F11 – F19 (excl. F17.2)
- Gastric or peptic ulcer disease/diseases of gastrointestinal tract: ICD-GM: K21, K25.4 – K25.9, K26.4 – K26.9, K27.4 – K27.9, K28.4 – K28.9, K29, K30, K64
- Heart failure: ICD-GM: I11.0, I13.0, I13.2, I25.5, I42, I43, I50
- History of major bleeding (hospitalization only): OPS: 8800

ICD-GM: D62, H21.0, H31.3, H35.6, H43.1, H45.0, I32.1, I60 - I62, J94.2, M25.0, S06.4, S06.5, S06.6, S06.8

- Hypertension: ICD-GM: 110 - 115, 167.4
- Hypothyroidism: ICD-GM: E00, E01.8, E02, E03, E89.0
- Inflammatory bowel disease: ICD-GM: K51, K52
- Ischemic stroke or transient ischemic attack:
 - ICD-GM: G45.0 G45.2, G45.4 G45.9, I63, I69.3, I69.4
- Systemic embolism:
 - ICD-GM: I74
- Other cerebrovascular disease: ICD-GM: I64 - I69 (excl. I69.3, I69.4)
- Liver disease:

ICD-GM: B18.0, B18.1, B18.2, I85, K70.0, K70.2, K70.3, K70.4, K70.9, K72.1, K73, K74, K75.4, K75.8, K76.0, K76.6, K76.9, Z94.4

- Hyperlipidemia: ICD-GM: E78.0 – E78.5
- Volume depletion:

ICD-GM: E86

- Other metabolic disorders: ICD-GM: E87
- Obesity:

ICD-GM: E66

- Peripheral artery disease:
 - ICD-GM: I70.2 I70.9, I71, I73.9
- Psychosis:

ICD-GM: F20, F22 – F25, F28, F29 – F31, F32.3 – F32.5, F33.3, F33.4, F34.8, F34.9, F39, F44.8

- Pulmonary disease: ICD-GM: I27, I28.9, J44
- Rheumatoid arthritis/collagen vascular disease:

ICD-GM: M05, M06, M08, L90.0, L94.0, L94.1, L94.3, M32 - M35, M45, M46, M48, M49

• Renal impairment:

ICD-GM: D63.1, E10.2, E11.2, E13.2, I12, I13, N02, N03, N04, N05, N07, N08, N14, N18.1-N18.4, N18.9, N19, Q61

- Acute kidney injury: ICD-GM: N17
- Tobacco abuse: ICD-GM: F17.2
- Other vascular disease: ICD-GM: I70.1, I72, I73.1, I73.8, I74, I79, K55.1, K55.8, K55.9, Z95
- Malignant cancer (excl. non-melanoma skin cancer) : ICD-GM: C00-C97 (excl. C44)
- Angiotensin-converting enzyme inhibitors or angiotensin-receptor blockers: ATC: C09
- Antiarrhythmics:

ATC: C01B

• Antidepressants:

ATC: N06A

- Antiplatelets: ATC: B01AC
- Antiulcer drugs (except proton-pump inhibitors): ATC: A02BA, A02BB, A02BX
- Beta blockers:

ATC: C07

- Calcium channel blockers: ATC: C08
- Diabetes drugs (incl. insulin): ATC: A10A, A10B
- Diuretics:

ATC: C03

- Erythropoietin-simulating agents: ATC: B03XA
- Estrogens: ATC: G03C, L02AA
- Lipid modifying agents: ATC: C10

- Non-steroidal anti-inflammatory drugs: ATC: M01A
- Proton-pump inhibitors:

ATC: A02BC

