9.3.4 Subpopulations and Subgroups

Subgroups and subpopulation are only build on the basis of conditions already present at index date.

The following subpopulations of special interest will be defined:

• Patients with renal impairment initiating either phenprocoumon or reduced doses of NOACs

Patients with renal impairment will be identified based on primary and secondary hospital diagnoses or verified ambulatory diagnoses in the baseline period according to Fleet et al. (9) and Nielsen et al. (4) (see definition of renal impairment as covariate in Annex 3: Additional information).

• Patients with chronic renal disease initiating either phenprocoumon or reduced dose of NOACs

Patients with chronic renal disease will be identified based on primary and secondary hospital diagnoses or verified ambulatory diagnoses (ICD 10 GM code N18.3 and N18.4) in the baseline period.

The following subgroups of special interest will be defined. Analyses will be conducted also including a test for effect modification (interaction):

• Frail patients

Frailty can be operationalized in several ways, but is commonly characterized by a set of signs and symptoms in geriatrics and gerontology research. While difficult to assess in administrative claims data, the recently validated claims based Frailty Indicator (10) will be used in this study. This algorithm is

validated using against the frailty phenotype, which is the most widely used instrument for assessing frailty. The frailty cut-off for this study will be 0.25 as the desire is to specifically identify frail individuals.

• Age group (<=79 vs. 80+ years)

Age will be assessed at the index date.

• Renal impairment

Patients with renal impairment will be identified based on primary and secondary hospital diagnoses or verified ambulatory diagnoses in the baseline period according to Fleet et al. (9) and Nielsen et al. (4) (see definition of renal impairment as covariate in Annex 3: Additional information).

• Prior IS or SE

Patients with IS, TIA or SE will be identified based on primary and secondary hospital diagnoses or verified ambulatory diagnoses in the baseline period according the definition for IS/TIA and SE as covariate (see Annex 3: Additional information).

• Reduced vs. standard dose of NOACs

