K27.4, K27.6, K28.0, K28.2, K28.4, K28.6, K29.0, K62.5, K66.1 K92.0, K92.1. K92.2, M25.0, N02, N42.1, N83.6, N85.7, N89.7, N93.0, N93.8, N93.9, N95.0, R04.0, R04.1, R04.2, R04.8, R04.9, R23.3, R31, R58, S06.4, S06.5, S06.6, S06.8

Section 9.3.3. Covariate definition

Operational definition of CHA2DS2-VASc Score:

Conditions	ICD-10 GM code	Assigned weights
Hypertension	I10 – I15, I67.4	1
Diabetes mellitus	E10 – E14	1
Heart failure	I11.0, I13.0, I13.2, I25.5, I42, I43, I50, I09.9	1
Age between 65 and 74 years		1
Vascular disease (previous MI, peripheral arterial disease or aortic plaque)	I21 – I23, I25.2, I70.0, I70.2 – I70.9, I71, I73.9	1
Stroke or TIA	G45.0 – G45.2, G45.4 – G45.9, I63, I69.3, I69.4, I64	2
Age \geq 75 years		2
Female sex		1

Operational definition of CHADS₂ Score:

Conditions	ICD-10 GM code	Assigned weights
Hypertension	I10 – I15, I67.4	1
Diabetes mellitus	E10 – E14	1
Heart failure	I11.0, I13.0, I13.2, I25.5, I42, I43, I50, I09.9	1
Stroke or TIA	G45.0 – G45.2, G45.4 – G45.9, I63, I69.3, I69.4, I64	2

Age ≥ 75	years
---------------	-------

1

Operational definition of modified HAS-BLED Score:

Criteria	ICD-10 GM / ATC /OPS code	Assigned weights
Hypertension	I10 – I15, I67.4	1
Liver or renal disease	B18.0, B18.1, B18.2, I85, K70.0, K70.2, K70.3, K70.4, K70.9, K72.1, K73, K74, K75.4, K75.8, K76.0, K76.6, K76.9, Z94.4, D63.1, E10.2, E11.2, E13.2, I12, I13, N02, N03, N04, N05, N07, N08, N14, N18.1-N18.4, N18.9, N19, Q61	1
Stroke history	I63, I69.3, I69.4, I64	1
Major bleeding event	OPS: 8800 ICD-GM: D62, H21.0, H31.3, H35.6, H43.1, H45.0, I32.1, I60 - I62, J94.2, M25.0, S06.4, S06.5, S06.6, S06.8	1
Alcohol abuse	F10	1
Non-steroidal anti-inflammatory drugs or antiplatelet	B01AC, M01A*	1
Age >65		1

Operational definition of claims based frailty indicator (10):

Criteria	ICD-10 GM / ATC /OPS code	Assigned weights
Impaired mobility	U50, Z99.3	1
Depression	F31, F32 – F34, F39, F43.1, F43.2,	1
Congestive heart failure	I11.0, I13.0, I13.2, I25.5, I42, I43, I50	
Parkinson's disease	G20-G22	

White race (yes vs. no)	N/A	
Arthritis (any type)	M05, M06, M08, L90.0, L94.0, L94.1, L94.3, M32 – M35, M45, M46, M48, M49	
Cognitive impairment	F01 – F05, F06.0, F06.7, F06.8, F07.0, F07.8, F09, G30, G31.0, G31.1, G31.8, R41	
Charlson comorbidity index (>0, 0)	As defined above	
Stroke	I60-I64, I69.0-4	1
Paranoia	F06.0, F06.2, F20, F22-F29, F32.3, F33.3, F44.8	
Chronic skin ulcer	170.24, 170.25, 183.0, 183.2, 187.21, L89, L97	
Male (yes vs. no)		

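### Two items of the frailty indicator in Annex 3 carry code lists that do not match their labels: TIA codes count as a musculoskeletal problem, and arthritis of any type is coded with the rheumatoid/collagen list

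*Protocol*

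**What the plan says.** Protocol section 9.3.4 makes frail patients one of six subgroups, each with a test for effect modification. It states that "the recently validated claims based Frailty Indicator (10) will be used in this study" and that "The frailty cut-off for this study will be 0.25 as the desire is to specifically identify frail individuals". Annex 3, under section 9.3.3, lists the 21 items and their codes.

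- The item for musculoskeletal problems opens with "G45, M12-M14, M24, M25, M36, M43, M46, M47.1, M47.8, M50-M54" and continues with further M codes, R26.2, R29.8 and Z87.3.
- The item *Arthritis (any type)* is coded "M05, M06, M08, L90.0, L94.0, L94.1, L94.3, M32 – M35, M45, M46, M48, M49".
- The item *Stroke* is coded "I60-I64, I69.0-4", without G45.

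Elsewhere in the same Annex:

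- The stroke-or-TIA component of CHADS2 and of CHA2DS2-VASc is coded "G45.0 – G45.2, G45.4 – G45.9, I63, I69.3, I69.4, I64".
- The covariate "Ischemic stroke or transient ischemic attack" uses the same G45 subcodes.
- The covariate *Rheumatoid arthritis/collagen vascular disease* is coded "M05, M06, M08, L90.0, L94.0, L94.1, L94.3, M32 - M35, M45, M46, M48, M49".

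**The concern.** Annex 3 fixes these lists, so a programmer who follows it will set the two items from the codes as written, whatever the labels say. A patient with a TIA code and no musculoskeletal diagnosis would have the musculoskeletal item set. A patient whose only arthritis code lies in M15–M19 would not have the arthritis item set, while a patient with L90.0 or M32 would.

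What is at stake is the frailty interaction test. TIA is part of the definition of another subgroup, prior IS or SE (section 9.3.4). If TIA also feeds frailty under a musculoskeletal label, a frail/non-frail contrast for IS/SE can partly reflect cerebrovascular history, and nothing in the item names would tell the reader so.

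**Working it through.** The protocol states no figure that could be reproduced here, so the check compares the code lists within Annex 3.

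**1. G45.** The musculoskeletal item names the whole category, G45.0 to G45.9. The Annex's TIA codes are G45.0–G45.2 and G45.4–G45.9. Every TIA code is therefore inside the musculoskeletal item, and the only extra subcode is G45.3. With ranges expanded, the item has 25 entries: G45, 21 M entries, and R26.2, R29.8 and Z87.3. One entry of 25 is out of place against the Annex's own use of it. Because the frailty stroke item omits G45, TIA has no stroke-labelled place in the indicator and enters under the musculoskeletal label.

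**2. Arthritis.** Each of the two lists expands to 15 entries: M05, M06, M08; L90.0, L94.0, L94.1, L94.3; M32, M33, M34, M35; M45, M46, M48, M49. They agree on 15 of 15. One list cannot define both arthritis of any type and a narrower covariate.

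- Eight of the 15 entries (four L codes and M32–M35) are the skin and connective-tissue part.
- M15–M19 (the osteoarthritis block of ICD-10) appear in no item and no covariate of the Annex.
- M12–M14 sit under the musculoskeletal item.
- M46 is in both items, so that single code sets both.

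**3. Share of the indicator.** Two of 21 items are affected.

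**4. Can the effect on frail status be derived?** That would need the weights of the two items and the rule linking the items to 0.25. In the text at hand no weight is legible for either row, and the protocol gives no formula. Two purely illustrative readings show how wide the range is:

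- If the score were an equal-weight fraction of 21 items, one item would move it by 1/21 = 0.048 and two by 2/21 = 0.095. Reaching 0.25 would need 0.25 × 21 = 5.25, that is 6 items. A wrongly set item would then matter only for patients already close to the cut-off.
- If an item counted as one raw point, it would exceed 0.25 alone.

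The lists do not show which reading, if either, applies.

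**The case against.** **The lists are mostly sound.** The musculoskeletal list has one misplaced entry, and the other 24 fit the label or are gait and history codes. The arthritis list does contain arthritis codes (M05, M06, M08, M45), and M12–M14 are elsewhere in the indicator. This stands, and it rules out saying that both items use lists for other conditions.

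**Stroke history already enters frailty by design.** The indicator has its own stroke item, so overlap with the prior IS or SE subgroup exists without G45, which only adds to it. Section 9.7.2 also plans to adjust for the section 9.3.3 covariates, which include ischemic stroke or TIA. That adjustment addresses TIA as a confounder but does not separate two mixed effect modifiers.

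**The source may use these codes.** The indicator's source publication is not available here, so the label rather than the list could be at fault. The fix has to allow for this. The conflict inside Annex 3 remains either way.

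**A stronger reading goes too far.** A reader might infer that the frail subgroup measures something other than frailty, or that thousands of patients are wrongly called frail. The protocol supports neither. Suppose 3–8% of patients had a G45 code at baseline and 40–60% of those had no other listed musculoskeletal code. The item would then be set by G45 alone in 0.03 × 0.40 = 1.2% to 0.08 × 0.60 = 4.8% of the 84,000 expected users (35,400 + 16,800 + 30,200 + 1,600), or about 1,000 to 4,000 patients. Both input ranges are assumptions with no basis in the protocol. The result counts item flags, not patients reclassified as frail.

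**A misprint is unlikely.** The item's list runs in alphanumeric order, and G45 stands in its proper place before M12.

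**Conclusion.** Both coding mismatches are established from Annex 3 alone: G45 conflicts with the Annex's own TIA definition, and the arthritis list is a copy of a narrower covariate. Two of 21 items therefore depart from their labels, and some patients may fall on the wrong side of 0.25. How many, and in which direction, cannot be derived.

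The importance is limited. Frailty is one subgroup factor, section 7 mentions frail patients only as an example, and the abstract states that p-values are not confirmatory. The primary objectives concern renal impairment and do not use this indicator. The point is a minor one, worth correcting because the error is specific and would otherwise be programmed as written. It assumes only that the labels state what the items are meant to capture. The reference to M15–M19 also relies on the ordinary meaning of those ICD-10 codes.

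**What to change.** Before the frail subgroup is derived:

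1. Remove G45 from the musculoskeletal item in Annex 3.
2. Give *Arthritis (any type)* its own list covering arthritis of any type, including M15–M19, and decide whether M46 should stay in both items.
3. Check both lists against the source indicator. If the source does use the present codes, keep them, say so in the Annex, and correct the labels so that TIA and the rheumatoid/collagen content are visible to the reader.

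The cost is two code-list corrections before programming. No new data are needed, and the sample size and primary analysis do not change.

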9.7.3 Sensitivity analysis

We will conduct three pre-defined sensitivity analyses to prove the consistency of our results. First, we will repeat the Cox regression analysis for IS/ SE as combined endpoint and ICH (primary objectives) as well as for the analysis of treatment discontinuation allowing for stockpiling of phenprocoumon and NOACs, i.e. if a prescription of the index drug is refilled before the estimated end of supply, the remaining supply of the prescription will be added to following prescription. Second, we will perform the Cox regression analysis for the outcomes ICH, IS, SE, severe IS, kidney failure, AKI and fatal bleeding excluding patients with a prior outcome event in the baseline period, i.e. major bleeding for ICH and fatal bleeding, IS or SE for IS and severe IS, SE (see covariate definition in Annex 3: Additional information). Third, we will repeat the Cox regression analysis for IS/ SE as combined endpoint and ICH analyses using the pDDD to calculate the supply for phenprocoumon as defined in section 9.3.1.

No actions will be taken to deal with missing data, since data from all dimensions is assumed to be complete.

All analysis will be performed using SAS Enterprise guide version 7.1 or R.

The statistical concept of the study described above will be supplemented by the more detailed statistical analysis plan.

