B01AF02	Apixaban	11376429	Eliquis 2,5 mg Filmtabletten Milinda	Reduced
B01AF02	Apixaban	11376435	Eliquis 2,5 mg Filmtabletten Milinda	Reduced
B01AF02	Apixaban	11376441	Eliquis 5 mg Filmtabletten Milinda	Standard
B01AF02	Apixaban	11376458	Eliquis 5 mg Filmtabletten Milinda	Standard
B01AF02	Apixaban	11524829	Eliquis 5 mg Axicorp	Standard
B01AF02	Apixaban	11524841	Eliquis 5 mg Axicorp	Standard
B01AF02	Apixaban	13578924	Eliquis 2,5 mg Axicorp	Reduced
B01AF03	Edoxaban	10714031	Lixiana 30 mg Filmtabletten	Reduced
B01AF03	Edoxaban	10714060	Lixiana 30 mg Filmtabletten	Reduced
B01AF03	Edoxaban	10714083	Lixiana 30 mg Filmtabletten	Reduced
B01AF03	Edoxaban	10714143	Lixiana 30 mg Filmtabletten	Reduced
B01AF03	Edoxaban	10714172	Lixiana 60 mg Filmtabletten	Standard
B01AF03	Edoxaban	10714255	Lixiana 60 mg Filmtabletten	Standard
B01AF03	Edoxaban	10714284	Lixiana 60 mg Filmtabletten	Standard
B01AF03	Edoxaban	10714309	Lixiana 60 mg Filmtabletten	Standard

B01AF03	Edoxaban	12749950	Lixiana 30 mg Axicorp	Reduced
B01AF03	Edoxaban	12749967	Lixiana 30 mg Axicorp	Reduced
B01AF03	Edoxaban	12749996	Lixiana 60 mg Axicorp	Standard
B01AF03	Edoxaban	12750002	Lixiana 60 mg Axicorp	Standard
B01AF03	Edoxaban	13695860	Lixiana 30 mg Kohl Ph.	Reduced
B01AF03	Edoxaban	13695877	Lixiana 60 mg Kohl Ph.	Standard

Section 9.3.2. Outcome definition

- Ischemic stroke (IS): ICD-GM: I63
- Severe ischemic stroke according to (8):

ICD-GM: I63 in combination with

OPS: 870, 871 (intubation/mechanical ventilation), 5431, 8017, 8018, 8123 (percutaneous endoscopic gastrostomy)

• Systemic embolism (SE):

ICD-GM: I74

- Intracranial hemorrhage (ICH): ICD-GM: I60 – I62
- Acute kidney injury (AKI) according to (14): ICD-GM: N17
- Kidney failure:

ICD-GM (hospital): N18.5, Z94.0

ICD-GM (ambulatory): N18.5, N18.9, N19, Z94.0 in combination with

OPS: 8853, 8854, 8855, 8857 OR

EBM: (**valid from Q1 2013 onwards**) 13602, 13610, 13611, 40815, 40816, 40817, 40818, 40819,40823, 40824, 40825, 40826, 40827, 40828, 40829, 40830, 40831, 40832, 40833, 40834, 40835, 40836, 40837, 40838

• Fatal bleeding:

OPS: 8800

ICD-GM: D62, H11.3, H21.0, H31.3, H35.6, H43.1, H45.0, H92.2, I32.1, I60, I61, I62, I85.0, J94.2, K22.6, K22.8, K25.0, K25.2, K25.4, K25.6, K26.0, K26.2, K26.4, K26.6, K27.0, K27.2,

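### The baseline major-bleeding list has none of the 25 gastrointestinal bleeding codes in the fatal-bleeding outcome, so prior gastrointestinal bleeds are only partly excluded and partly adjusted for

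*Protocol*

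**What the plan says.** **Baseline list.** Annex 3 (Section 9.3.3, covariate definition) names the item "History of major bleeding (hospitalization only"), gives the procedure code OPS 8800 and continues with "ICD-GM: D62, H21.0, H31.3, H35.6, H43.1, H45.0, I32.1, I60 - I62, J94.2, M25.0, S06.4, S06.5, S06.6, S06.8". The major-bleeding row of the modified HAS-BLED table carries the same codes.

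**Outcome list.** Annex 3 (Section 9.3.2, outcome definition) gives the fatal-bleeding codes. They include "I85.0, J94.2, K22.6, K22.8, K25.0, K25.2, K25.4, K25.6, K26.0, K26.2, K26.4, K26.6, K27.0, K27.2" and then "K27.4, K27.6, K28.0, K28.2, K28.4, K28.6, K29.0, K62.5, K66.1 K92.0, K92.1. K92.2". Under Section 9.3.2 the code must be the primary discharge diagnosis, and death must follow in hospital or within 30 days of discharge.

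**Where the baseline list is used.** Section 9.7.3 describes a second sensitivity analysis that leaves out patients with an outcome event in the baseline period. It specifies the prior event as "i.e. major bleeding for ICH and fatal bleeding" and refers to the Annex 3 covariate definition. Section 9.7.2 takes the confounders for the regression models and the propensity score from Section 9.3.3, which lists history of major bleeding.

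The protocol gives no reason why the baseline list is narrower than the outcome list.

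**The concern.** A previous bleed plausibly influences both the choice of anticoagulant and the risk of a later bleed. If gastrointestinal bleeds are left out of the bleeding history, two things follow.

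- **Exclusion.** The sensitivity analysis for fatal bleeding is meant to remove patients who already had the event. A patient admitted at baseline under K92.2 who later dies of a K92.2 bleed can remain in it.
- **Adjustment.** The Cox models, the weights and the matching all draw on the same bleeding-history variable. The HAS-BLED score cannot compensate, because its bleeding item uses the same codes.

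Fatal bleeding is an outcome under both the secondary objectives (Section 8.2) and the other objectives (Section 8.3). ICH is a primary outcome, and its models use the same confounder set.

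**Working it through.** The protocol states no figure to reproduce here. The check is a comparison of code lists, followed by an illustrative bias calculation.

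**Step 1: size of the lists (Annex 3, ICD entries, I60 to I62 counted as three).**

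- Fatal-bleeding outcome: 60
- History of major bleeding: 16, all of them also in the outcome list
- In the outcome list only: 60 − 16 = 44

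OPS 8800 is in both lists.

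**Step 2: gastrointestinal codes among the 44.**

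- I85.0: 1
- K22.6, K22.8: 2
- K25, K26, K27, K28, each with .0, .2, .4, .6: 4 × 4 = 16
- K29.0, K62.5, K66.1: 3
- K92.0, K92.1, K92.2: 3
- Total: 1 + 2 + 16 + 3 + 3 = 25 (24 if K66.1 is not counted as gastrointestinal)

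None of the 25 is in the baseline list. The other 44 − 25 = 19 are eye, ear, urogenital, R04.x and unspecified bleeding codes.

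**Step 3: do other Annex 3 comorbidity covariates pick up the 25?**

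| Covariate | Codes caught | Number |
|---|---|---|
| Ulcer / gastrointestinal disease | K25.4, K25.6, K26.4, K26.6, K27.4, K27.6, K28.4, K28.6, K29.0 | 9 |
| Liver disease (contains I85) | I85.0 | 1 |
| None | K22.6, K22.8, K25.0, K25.2, K26.0, K26.2, K27.0, K27.2, K28.0, K28.2, K62.5, K66.1, K92.0, K92.1, K92.2 | 15 |

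Check: 9 + 1 + 15 = 25. The ulcer covariate also contains K21, K30 and K64, so it is not a bleeding variable. Neither of these two covariates plays any part in the Section 9.7.3 exclusion for fatal bleeding.

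**Step 4: what is still caught.** D62 and OPS 8800 are in the baseline list. A gastrointestinal bleed whose hospital stay also carries either code counts as history of major bleeding. The protocol does not say how often that happens.

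**Step 5: ICH.** The ICH outcome is I60 to I62, and all three are in the baseline list. The ICH exclusion therefore covers the same event.

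**Step 6: illustrative size of the confounding.** The protocol gives no prevalence, imbalance or hazard for prior gastrointestinal bleeding. The following are assumptions: prevalence p of 2% to 4%, a difference of 1 to 2 percentage points between drugs, and a hazard ratio R of 2 to 4 for later bleeding. If the factor were wholly unadjusted, the bias factor in the HR would be (1 + p1(R − 1)) / (1 + p0(R − 1)).

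| p0 | p1 | R | Bias factor |
|---|---|---|---|
| 0.02 | 0.03 | 2 | 1.03 / 1.02 = 1.010 |
| 0.02 | 0.04 | 2 | 1.04 / 1.02 = 1.020 |
| 0.02 | 0.03 | 4 | 1.09 / 1.06 = 1.028 |
| 0.02 | 0.04 | 4 | 1.12 / 1.06 = 1.057 |

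With the imbalance reversed, the largest case becomes 1.06 / 1.12 = 0.946. Steps 3 and 4 show that the factor is not wholly unadjusted, so under these inputs the figures are upper bounds.

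**The case against.** **The lists serve different purposes.** The outcome list is filtered by primary diagnosis and death, so broad codes do little harm there. Covariates use primary and secondary diagnoses (Section 9.3.3), so a narrower list for a variable called major bleeding can be defended. This stands as an argument against copying the whole outcome list. It does not explain why gastrointestinal bleeding is absent, and the protocol does not offer it as a reason.

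**A prior fatal bleed cannot exist.** Some proxy is unavoidable, and Section 9.7.3 names one and applies it. A reader might infer that the sensitivity analysis fails to do what it says. The text does not support that: it excludes exactly what Annex 3 calls major bleeding. What stands is that this proxy fits the outcome poorly, because 25 of the 60 outcome entries have no counterpart in it.

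**Other covariates help.** A reader might also infer that prior gastrointestinal bleeding is missed altogether or left largely unadjusted. The documents do not show this. Stays with D62 or OPS 8800 are caught, and 10 of the 25 codes enter through other covariates. Anemia, proton-pump inhibitors, other antiulcer drugs, non-steroidal anti-inflammatory drugs, antiplatelets and number of hospitalizations are also in Section 9.3.3 and are plausible correlates. None of them is a bleeding history, so adjustment is partial.

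**The effect is small.** This stands. The bias inputs are assumed, and the abstract says that p-values and confidence intervals must not be read as confirmatory.

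**Conclusion.** The point holds as an unexplained mismatch between two code lists in the same annex. None of the 25 gastrointestinal outcome codes is in the baseline list or the HAS-BLED bleeding item, and 15 are in no listed comorbidity covariate.

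- **Fatal bleeding:** the prior-event exclusion leaves in gastrointestinal bleeds coded without D62 or OPS 8800, and adjustment for them is partial.
- **ICH:** the exclusion covers the same-event codes. Only confounding control is affected, so the primary ICH sensitivity analysis should not be read as failing to exclude prior ICH.

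The size of any bias cannot be derived from the protocol. Under the assumptions in the working it is about 1% to 6% in either direction if nothing else adjusts for the factor, and less to the extent that other covariates do. This is a minor point, worth correcting because the correction is simple.

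**What to change.** Add I85.0, K22.6, K22.8, K25 to K28 (.0, .2, .4, .6), K29.0, K62.5, K66.1 and K92.0 to K92.2, as hospital diagnoses in the baseline period, to three places:

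1. the history-of-major-bleeding covariate;
2. the major-bleeding item of the modified HAS-BLED score;
3. the prior-event exclusion for fatal bleeding in Section 9.7.3.

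Section 9.7.3 points ICH and fatal bleeding to the same covariate. It should therefore name the list for each outcome; otherwise widening the covariate also widens the ICH exclusion.

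The full fatal-bleeding list should not be imported. With secondary diagnoses allowed, codes such as R04.0, H11.3, R23.3 and R31 would count as major bleeding. N02 already defines renal impairment in Annex 3 and scores under the renal item of HAS-BLED. It would score twice and flag members of the primary-objective population as prior bleeders.

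If the sponsor prefers the short list, the protocol should say why.

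The cost is a code-list edit on data already held. The covariate becomes broader and some more patients leave the sensitivity analysis; the protocol does not allow that number to be estimated.
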